### **3.4. Safety Monitoring and the E-DMC**

From the time of study initiation through completion of the study, the sponsor will conduct routine safety monitoring of the data per the safety review plans. In addition, the E-DMC will periodically review safety data as outlined in [Section 3.4.1](#).

#### **3.4.1. External Data Monitoring Committee (E-DMC)**

The E-DMC will include experts in the field of neuromuscular diseases and/or statistics. Members of the E-DMC will not be Pfizer employees. The E-DMC will be responsible for ongoing efficacy and safety monitoring and its reviews will include aggregate safety, targeted medical events of special interest including liver toxicity, and serious adverse event (SAE) data. Additional ad hoc safety reviews may be performed as described in the E-DMC charter.

Following each data review, the E-DMC will provide a recommendation to the sponsor management to continue the study, modify the study and then continue (eg, but not limited to terminate a dose level, remove the liver MRI or other monitoring assessments), or stop the study (eg, due to safety). The recommendations made by the E-DMC to alter the conduct of the study will be forwarded to the sponsor management for final decision. The sponsor management will forward such decisions, which may include summaries of aggregate analyses of endpoint events and of safety data that are not endpoints, to regulatory authorities, as appropriate. At any time the E-DMC may indicate that the limit of safety and/or tolerability has been reached and that any of the dose levels will be removed from the study.

Additional details of the type, timing and responsibilities of the E-DMC will be included in the E-DMC charter.

## **4. SUBJECT SELECTION**

This study can fulfill its objectives only if appropriate subjects are enrolled. The following eligibility criteria are designed to select subjects for whom participation in the study is considered appropriate. All relevant medical and nonmedical conditions should be taken into consideration when deciding whether a particular subject is suitable for this protocol.

### **4.1. Inclusion Criteria**

Subject and caregiver eligibility should be reviewed and documented by an appropriate member of the investigator's study team before subjects are included in the study.

Subjects must meet all of the following inclusion criteria to be eligible for enrollment into the study:

1. Subjects with Duchenne muscular dystrophy who enrolled and completed through Week 97 of Study B5161002.
2. Evidence of a personally signed and dated informed consent document (ICD) indicating that the subject's parent or legal guardian/caregiver has been informed of all pertinent aspects of the study. Subjects may be required to provide assent in compliance with local regulations and IRB requirements.
3. Subjects and their legal guardians/caregivers who are willing and able to comply with scheduled visits, treatment plan, laboratory tests, and other study procedures.
4. The following inclusion criteria will be assessed using data from the B5161002 study, and if data are unavailable, these assessments must be completed prior to enrollment:
  - a. Adequate hepatic function on screening laboratory assessments from the Week 97 visit.
  - b. GLDH  $\leq$  20 units/liter (2 x upper limit of normal [ULN]) from the Week 97 visit.
  - c. Iron content estimate on the liver MRI within the normal range as determined by R2\* value (R2\* $\leq$ 75 Hz at 1.5 T or R2\* $\leq$ 139 Hz at 3.0 T) from the Week 93 visit.

#### **4.2. Exclusion Criteria**

The following exclusion criteria will be assessed using Week 97 data from the B5161002 study, but if unavailable, these assessments must be completed prior to enrollment:

1. Unwilling or unable (eg, metal implants) to undergo examination with closed MRI. If subjects required sedation in the B5161002 study they will be permitted to enroll in the OLE. In the event that a subject becomes intolerant to MRI scanning, during the OLE, the subject may be separately consented to be administered sedation in order to complete the MRI.
2. All male subjects who are able to father children and are sexually active and at risk for impregnating a female partner, who are unwilling or unable to use with their female partner(s) a highly effective method of contraception consistently and correctly for the duration of the active treatment period and through the final study visit. In addition, all sexually active male subjects who are unwilling or unable to prevent potential transfer of and exposure to drug through semen to their partners by using a condom consistently and correctly, beginning with the first dose of investigational product and continuing through the final study visit.
3. Subjects who are investigational site staff members directly involved in the conduct of the study and their family members, site staff members otherwise supervised by the Investigator, or subjects who are related to Pfizer employees directly involved in the conduct of the study.

4. Other severe acute or chronic medical or psychiatric condition or laboratory abnormality that may increase the risk associated with study participation or investigational product administration or may interfere with the interpretation of study results and, in the judgment of the investigator, would make the subject inappropriate for entry into this study.
5. Participation in other studies involving investigational drug(s), with the exception of B5161002, for a minimum of 30 days or within 5 half-lives (whichever is longer) prior to signing the informed consent and/or during study participation.
6. History of allergic or anaphylactic reaction to a therapeutic or diagnostic protein or additives of this investigational product (histidine, sucrose, edetic acid [ethylenediaminetetraacetic acid], and polysorbate 80).

Note: Results considered by the investigator to be transient and inconsistent with the subject's clinical condition may be repeated once during the screening period for confirmation of eligibility. The reason for repeating the assessment should be documented.

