#### **1.4. Rationale for Dosage Selection and Method of Administration**

The dose for each subject will be based on their individual maximum tolerated dose (MTD) up to 40 mg/kg from Study B5161002. This study will use the same route and frequency of administration as Study B5161002. IV was chosen as the route of administration for B5161002 to support the large dose that will be required to obtain the targeted GDF-8 coverage. The frequency of administration was chosen as 4 weeks to achieve targeted GDF-8 coverage but also to reduce the burden on subject travel to study sites.

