#### **1.6.3. CCI Sexual Development**

CCI

Given the target population of DMD pre-pubertal boys, this effect needs to be monitored. Tanner staging and testicular volume will be used to monitor pubertal development, in addition to the measurement of sex hormone levels and bone age with a wrist and hand X-ray assessment. Should boys reach sexually maturity during the trial as indicated by a Tanner Stage V rating, monitoring will no longer be mandatory.

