### **2.2.2.2. PK and Immunogenicity**

Trough serum PF-06252616 concentrations for all subjects receiving active drug.

- Incidence of ADA and NAb.

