#### **4.4.3. Contraception**

All male subjects who are able to father children and are sexually active and at risk for impregnating a female partner, must agree to use with their female partner(s) a highly effective method of contraception consistently and correctly for the duration of the active treatment period and through the final study visit. The investigator or his or her designee, in consultation with the subject and/or the subject's legal guardian, will confirm the subject has selected the most appropriate method of contraception for the individual subject and his partner from the permitted list of contraception methods (see below) and instruct the subject in its consistent and correct use. Subjects need to affirm that they meet the criteria for correct use of at least 1 of the selected methods of contraception. The investigator or his/her designee will discuss the need to use highly effective contraception consistently and correctly throughout the study and document such conversation in the subject's chart. In addition, the investigator or his/her designee will instruct the subject and/or subject's legal guardian to call immediately if the selected birth control method is discontinued or if partner pregnancy is known or suspected in the subject's partner.

Highly effective methods of contraception are those that, alone or in combination, result in a failure rate of less than 1% per year when used consistently and correctly (ie, perfect use) and include the following:

1. Established use of oral, inserted, injected, implanted or transdermal hormonal methods of contraception are allowed provided the subject plans to remain on the same treatment throughout the entire study and has been using that hormonal contraceptive for an adequate period of time to ensure effectiveness.
2. Correctly placed copper-containing intrauterine device (IUD).
3. Male condom or female condom used WITH a spermicide (ie, foam, gel, film, cream, or suppository). For countries where spermicide is not available or condom plus spermicide is not accepted as highly effective contraception, this option is not appropriate.
4. Male sterilization with absence of sperm in the postvasectomy ejaculate.
5. Bilateral tubal ligation / bilateral salpingectomy or bilateral tubal occlusive procedure (provided that occlusion has been confirmed in accordance with the device's label).

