In addition, all sexually active male subjects must agree to prevent potential transfer of and exposure to drug through semen to their partners by using a condom consistently and correctly, beginning with the first dose of investigational product and continuing through the final study visit.

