### 6.3. Subject Withdrawal

Subjects may withdraw from the study at any time at their own request, or they may be withdrawn at any time at the discretion of the investigator or sponsor for safety or behavioral reasons, or the inability of the subject/caregiver to comply with the protocol-required schedule of study visits or procedures at a given study site. Subjects may be withdrawn from the OLE study should the parent study, B5161002 fail to meet its planned study objectives, is terminated early for other reasons (eg, sponsor decision) or the drug is commercialized. If a subject does not return for a scheduled visit, every effort should be made to contact the subject. All attempts to contact the subject and information received during contact attempts must be documented in the subject's medical records. In any circumstance, every effort should be made to document subject outcome, if possible. The investigator should inquire about the reason for withdrawal, request that the subject to return for a final visit, if applicable, and follow-up with the subject regarding any unresolved AEs.

If the subject withdraws from the study and also withdraws consent for disclosure of future information, no further evaluations should be performed and no additional data should be collected. The sponsor may retain and continue to use any data collected before such withdrawal of consent.

In the event of clinically important treatment-emergent suicidal ideation or suicidal behavior, the subject will be withdrawn from the study and will receive the appropriate medical care. The Investigator will follow up until the subject's condition has stabilized. Additionally, a risk assessment or evaluation of suicide risk will be completed by a child and adolescent mental health provider as part of the psychiatric evaluation and assessment of subject safety. Refer to [Section 7.2.7](#).

Clinically important suicidality includes but is not limited to:

- a. Suicidal behavior (with or without intent of suicide or serious self-harm).
- b. Determination of “yes” on question 4 (Active Suicidal Ideation with Some Intent or Act, Without Specific Plan) for the Suicidal Ideation section of the C-SSRS.

- c. Determination of “yes” on question 5 (Active Suicidal Ideation with Specific Plan and Intent) for the Suicidal Ideation section of the C-SSRS.

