- d. Determination of “yes” on the question of Actual Attempt, Interrupted Attempt, Aborted Attempt, or Preparatory Acts or Behavior for Suicidal Behavior section of C-SSRS.
- e. Acute suicidality to such a degree that precaution against suicide must be exercised.

At the time of withdrawal, procedures outlined in the early withdrawal visit should be performed as detailed in the [Schedule of Activities](#) and [Assessments](#).

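### Condom use, and on the plain reading contraception, end at the final study visit with no interval after the last dose, so an early withdrawer can be released 0 to 27 days after an infusion

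*Protocol*

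**What the plan says.** Exclusion criterion 2 in section 4.2 requires sexually active subjects to protect partners by "using a condom consistently and correctly, beginning with the first dose of investigational product and continuing through the final study visit". Section 4.4.3 imposes the same duty and gives its purpose: these subjects "must agree to prevent potential transfer of and exposure to drug through semen to their partners". Highly effective contraception, for subjects able to father children, is required "for the duration of the active treatment period and through the final study visit". The active treatment period is not defined, and nothing in the protocol carries either duty past the final visit.

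On leaving the study, section 6.3 states that "Subjects may withdraw from the study at any time at their own request" and that "At the time of withdrawal, procedures outlined in the early withdrawal visit should be performed". The last columns of the Schedule of Activities are Week 193 and Early Withdrawal; there is no post-treatment follow-up visit.

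On drug presence, section 1.4 says "The frequency of administration was chosen as 4 weeks to achieve targeted GDF-8 coverage", and section 2.2.2.2 makes pre-dose levels an endpoint: "Trough serum PF-06252616 concentrations for all subjects receiving active drug".

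**The concern.** The condom rule exists to stop partners being exposed to drug, so its end should depend on how long drug remains after the last infusion. It is tied instead to a visit that, for a withdrawing subject, has no fixed relation to dosing. A subject can follow the rule to the letter and be released days after a dose of up to 40 mg/kg.

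Early exit is foreseen, and not only by individual choice. Sections 3.2 and 6.3 allow withdrawal of subjects if the parent study fails its objectives or is stopped, and section 14 lets the sponsor end the study at its discretion. Such a stop could release several subjects mid-cycle together.

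Those at stake are partners outside the trial. Section 8.10 deals with a pregnancy after it has occurred and does not prevent the exposure.

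**Working it through.** The protocol states no figure for this interval, so there is none to reproduce. The check is date arithmetic on the Schedule of Activities.

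**Inputs**
- Dosing interval: 4 weeks (section 1.4). The Year 1 dosing days 1, 29, 57, …, 337 are each 28 days apart.
- End of both duties: the final study visit (sections 4.2 and 4.4.3).
- Early-withdrawal visit: at the time of withdrawal, with no minimum time since the last infusion (section 6.3).
- Last marked dose for a completer: Week 189, Day 1317. Final visit: Week 193, Day 1345, with no dose marked (Years 2 to 4 flowchart, as extracted).

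**Early withdrawer.** Let the last dose fall on day *d*, with the next due on *d* + 28. Withdrawal before the next dose falls on *d* + 0 to *d* + 27.
- Time from last dose to release: 0 to 27 days.
- Shortfall against one 28-day interval: 28 − 27 = 1 day to 28 − 0 = 28 days.

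**Completer.**
- Time from last dose to release: 1345 − 1317 = 28 days.
- Shortfall: 28 − 28 = 0 days.
- With ±3 days at each of the two visits the gap is 28 − 6 = 22 to 28 + 6 = 34 days, so an individual completer could be up to 28 − 22 = 6 days short.

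**Is drug expected during that time?** Section 1.4 chose the 4-week interval to maintain target coverage, and the protocol measures trough concentrations just before the next dose. By its own design, the protocol expects drug across the interval in which an early withdrawer can be released.

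**Would 28 days be enough?** The protocol cannot answer this. As an illustration only, assume first-order elimination with half-lives of 14, 21 or 28 days; none of these is a protocol figure. The fraction of the post-dose level left at day *t* is 0.5^(*t* / half-life).

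| Assumed half-life | Left at day 27 | Left at day 28 | Five half-lives |
|---|---|---|---|
| 14 days | 26% | 25% | 70 days |
| 21 days | 41% | 40% | 105 days |
| 28 days | 51% | 50% | 140 days |

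On any of these assumptions, 28 days is a minimum and not a washout.

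**The case against.** The strongest objection is that adequacy cannot be judged here. The half-life and reproductive-toxicity data would sit in the Investigator's Brochure, and the text on sexual development in section 1.6.3 is redacted. The 28-day benchmark is also not the protocol's. Section 1.4 chose 4-weekly dosing for coverage in the patient and to limit travel, not as a limit on partner exposure, and troughs are measured in the patient's serum. If drug can still be measured at day 28, release at day 28 is not shown to be safe either. The only post-dose interval for follow-up in the protocol is the 84-day SAE reporting period in section 8.2, which is not linked to contraception.

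Much of this stands. The distance from 28 days is not a measure of risk, and no adequate interval can be derived. The 84 days cannot simply be borrowed, though they show that the protocol can count from the last dose. What the objection does not remove is that the condom rule, followed exactly, can lapse while the protocol expects drug to be present. That holds whatever the half-life proves to be, and it is why 28 days is proposed only as a floor.

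Two further points are fair. Release at 0 days is an extreme, needing the infusion and the final visit on one day; a subject who declines an infusion on its due date is already at 28 days. Reach is also small: section 1.6.3 reads "Given the target population of DMD pre-pubertal boys", and only sexually active subjects who leave within a cycle are affected. Even so, participation can last up to 4 years, and the protocol itself provides for subjects reaching Tanner Stage V and for re-consent at the age of majority.

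**Conclusion.** The concern holds. As written, a sexually active subject who withdraws before his next infusion is due can be released from condom use 0 to 27 days after a dose, 1 to 28 days short of one dosing interval. The same applies to contraception if the undefined active treatment period is read as ending no later than the final visit. Completers have a nominal 28 days. That figure depends on the Years 2 to 4 dosing row being correctly extracted; the row also marks no dose at Weeks 97 and 145, so it deserves checking against the source.

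This is a weakness in a design choice, not a contradiction: sections 4.2 and 4.4.3 agree with each other. The number of subjects affected is not given and is probably small. It should be corrected because the rule can miss its own stated purpose and the correction is cheap. Confidence is medium, since the adequate interval depends on data outside the protocol.

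**What to change.** In section 4.2 (criterion 2) and section 4.4.3, end both condom use and highly effective contraception at the later of (a) the final study visit and (b) a fixed number of days after the last administration of investigational product. Set that number at 28 or more, with the sponsor choosing it from its elimination data. State that it applies to subjects who withdraw early, to those released by a sponsor stop, and to those who do not return for a visit.

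The cost is an amendment and matching consent and assent wording. At the 28-day floor, the added burden is 28 − 27 = 1 to 28 − 0 = 28 days for the early withdrawers concerned, and nominally 0 days for completers. A longer interval would extend the duty for both groups. No visit, sample or procedure is added.

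Enforcement after a subject has left rests on counselling, which section 4.4.3 already requires to be documented, so the end date should be part of that discussion.

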#### **4.3. Enrolment**

Subjects will be enrolled into the study provided they have satisfied all eligibility criteria. In order to provide the screening data from Study B5161002 to Study B5161004, and for programming to recognize the continuation of the subject, the site will complete an electronic case report form (eCRF) where subject numbers are recorded for both the parent Study B5161002 and OLE Study B5161004.

#### **4.4. Lifestyle Guidelines**

The following guidelines are provided:

##### **4.4.1. Meals and Dietary Restrictions**

Subjects should maintain their normal dietary intake throughout the study with the following exceptions:

- Subjects will be asked to fast for at least 8 hours prior to collection of blood to evaluate serum ferritin, serum iron, TIBC and % transferrin saturation.
- Subjects should avoid large meals for at least 2 hours prior to the DXA scan. Juice, water and small snacks may be permitted. Subjects should be in a state of euhydration. No calcium supplements should be taken within 24 hours of a DXA scan.
- Two days prior to collection of stool sample for fecal occult blood testing, *whenever possible*, subjects should refrain from eating red meat, turnips, horseradish, or medications containing aspirin or vitamin C and should consume only small amounts of chicken, canned tuna fish, peanuts, popcorn, bran cereal, vegetables and fruit.

#### **4.4.2. Activity**

Subjects should be instructed to continue with routine physical therapy including stretching or use of orthoses to prevent or minimize contractures or muscle deformities.

Subjects will be instructed to maintain normal activity levels and avoid activities that are not part of their normal daily routine within 24 hours of study visits where imaging or functional assessments will be performed.

#### **4.4.3. Contraception**

All male subjects who are able to father children and are sexually active and at risk for impregnating a female partner, must agree to use with their female partner(s) a highly effective method of contraception consistently and correctly for the duration of the active treatment period and through the final study visit. The investigator or his or her designee, in consultation with the subject and/or the subject's legal guardian, will confirm the subject has selected the most appropriate method of contraception for the individual subject and his partner from the permitted list of contraception methods (see below) and instruct the subject in its consistent and correct use. Subjects need to affirm that they meet the criteria for correct use of at least 1 of the selected methods of contraception. The investigator or his/her designee will discuss the need to use highly effective contraception consistently and correctly throughout the study and document such conversation in the subject's chart. In addition, the investigator or his/her designee will instruct the subject and/or subject's legal guardian to call immediately if the selected birth control method is discontinued or if partner pregnancy is known or suspected in the subject's partner.

Highly effective methods of contraception are those that, alone or in combination, result in a failure rate of less than 1% per year when used consistently and correctly (ie, perfect use) and include the following:

1. Established use of oral, inserted, injected, implanted or transdermal hormonal methods of contraception are allowed provided the subject plans to remain on the same treatment throughout the entire study and has been using that hormonal contraceptive for an adequate period of time to ensure effectiveness.
2. Correctly placed copper-containing intrauterine device (IUD).
3. Male condom or female condom used WITH a spermicide (ie, foam, gel, film, cream, or suppository). For countries where spermicide is not available or condom plus spermicide is not accepted as highly effective contraception, this option is not appropriate.
4. Male sterilization with absence of sperm in the postvasectomy ejaculate.
5. Bilateral tubal ligation / bilateral salpingectomy or bilateral tubal occlusive procedure (provided that occlusion has been confirmed in accordance with the device's label).

In addition, all sexually active male subjects must agree to prevent potential transfer of and exposure to drug through semen to their partners by using a condom consistently and correctly, beginning with the first dose of investigational product and continuing through the final study visit.

